From the plasma concentration-time data, the following pharmacokinetic parameters will be determined, as data permit: maximum observed plasma concentration (C_{max}), time to C_{max} (t_{max}), area under the plasma concentration time curve [AUC(0-t), AUC(0- τ), and AUC(0- ∞)], and apparent terminal phase half-life (t_{1/2}). Trough concentration (C_T) samples collected on the specified days may be used to assess attainment of steady state. To estimate the extent of accumulation after repeat dosing, the observed accumulation ratio for AUC (R_o) and C_{max} (R_{Cmax}) may be determined. To estimate the pharmacokinetic linearity, the state ratio (R_{ss}) may be determined. From the urine concentration data, the following pharmacokinetic parameters will be determined, as data permit: urinary excretion of unchanged drug (A_e), fraction of the dose excreted in the urine (f_e), and the renal clearance (C_{Lr}).

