7.2.1.3. Pharmacokinetic Parameters

7.2.1.3.1. Deriving Pharmacokinetic Parameters

- Refer to [Appendix 4](#): Data Display Standards & Handling Conventions (Section 10.4.3. Reporting Process & Standards).
- Plasma GSK3036656 concentration-time data will be analyzed by non-compartmental methods according to current working practices with WinNonlin 5.2 or higher.
- Non-compartmental analysis will be performed in accordance with GSK PK Guidance document GUI_51487.
- All calculations of non-compartmental parameters will be based on actual sampling times recorded during the study.
- Pharmacokinetic parameters described in [Table 5](#) will be determined from plasma concentration-time data and urine concentration data, as data permits.

Table 5 Derived Pharmacokinetic Parameters

Parameter	Parameter Description
AUC(0-t)	Area under the concentration-time curve from time zero to the time of the last quantifiable concentration (C(t)) will be calculated using the linear trapezoidal rule for each incremental trapezoid and the log trapezoidal rule for each decremental trapezoid.
AUC(0-∞)	Area under the concentration-time curve extrapolated to infinity calculated as: $\text{AUC} = \text{AUC}(0-t) + C(t) / \lambda_z$
AUC(0-24h)	Area under the concentration-time curve from time zero to 24 hours post-dose
AUC(0-τ)	AUC from time zero during a dosing interval of duration “τ”
AUC(Ro)	Observed accumulation ratio (Ro) for AUC will be calculated as follows: $\text{Day 14 AUC}(0-\tau) / \text{Day 1 AUC}(0-\tau)$
Ae	Urinary excretion of unchanged drug
Cmax	Maximum observed blood concentration, determined directly from the concentration-time data.

Parameter	Parameter Description
Ctrough	Pre-dose observed concentration, will be obtained directly from the concentration-time data.
CLr	Renal clearance
Fe	Fraction of the dose excreted in the urine
Lambda_z	The first order rate constant associated with the terminal (log-linear) portion of the concentration-time curve.
Rss	Steady state ratio (Rss) will be calculated as follows: Day 14 AUC(0- τ)/Day 1 AUC(0- ∞)
RCmax	Observed accumulation ratio for Cmax (RCmax) will be calculated as follows: Day 14 Cmax/Day 1 Cmax
tmax	Time to reach Cmax, determined directly from the concentration-time data.
t _{1/2}	Apparent terminal phase half-life will be calculated as: $t_{1/2} = \ln 2 / \text{Lambda}_z$ (NOTE: Lambda_z is the terminal phase rate constant).

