7.2.1.3.2. Statistical Analysis of Pharmacokinetic Parameters

For each of the parameters AUC (AUC(0- ∞), AUC (0- t), AUC(0- τ), AUC(Ro)), RCmax, Rss, Ct, Ae, fe, CLr and Cmax the following summary statistics will be calculated and tabulated by dose group for study Part A and Part B separately:

- **Untransformed Data:** N, n, arithmetic mean, 95% confidence interval (CI) for the arithmetic mean, SD, median, minimum, maximum.
- **Log_e-transformed Data:** Geometric mean, 95% CI for the geometric mean, SD of log_e-transformed data and %CVb.

For tmax, and t_{1/2} the summary statistics specified for untransformed data above will be generated.

The following pharmacokinetic statistical analyses will only be performed, if sufficient data is available (i.e. if subjects have well defined plasma profiles). Pharmacokinetic analysis will be the responsibility of the Clinical Pharmacology Modeling and Simulation Department, (CPMS) and Statistical analyses of the pharmacokinetic parameter data will be the responsibility of QSI Stats & Programming.

Pharmacokinetic Statistical Analyses (Dose Proportionality - Single and Repeat Dose Study Phases)	
Endpoint(s)	

 • Single Dose: AUC(0-t), AUC(0-∞) and Cmax • Repeat Dose : AUC(0-τ) and Cmax 	
Model Specification	

 • Will be statistically analysed using the power model • $y = \alpha^* \text{dose}^\beta$ 
Where y =PK parameter being analyzed and α= subject
 
 • Log_e transformed data will be analysed by fitting the following terms in the mixed effect model: 
 • Fixed effect: log_e (dose) • Random effect: Subject 	
Model Checking & Diagnostics	

 • Refer to Appendix 8: Model Checking and Diagnostics for Statistical Analyses. 	
Model Results Presentation	
Estimates of the mean slopes of log _e (dose) will be reported along with corresponding 90% confidence intervals (slope≈1 implies dose proportionality).	

Pharmacokinetic Statistical Analyses (Food Effect - Single Dose Study Phase)	
Endpoint(s)	

 • AUC(0-t), AUC(0-∞), Cmax and t_{1/2} 	
Model Specification	

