
 • Will be statistically analysed using a mixed model (MM) ANOVA. • Fixed, categorical effect : day • Random Effect : Subject 
AUC(0-inf) on Day 1 will be the reference phase in the analysis, while AUC(0- τ) on Day 14 will be the test phase, using log-transformed AUC.
	

 • The Kenward and Roger method for approximating the denominator degrees of freedom and correcting for bias in the estimated variance-covariance of the fixed effects will be used. • An unstructured covariance structure for the G matrix will be used. 
 ◦ In the event that this model fails to converge, alternative covariance structures may be considered such as VC or CS. ◦ Akaike's Information Criteria (AIC) will be used to assist with the selection of covariance structure. 	
Model Checking & Diagnostics	

 • Refer to Appendix 8: Model Checking and Diagnostics for Statistical Analyses. 	
Model Results Presentation	

 • The time invariance ratio of GSK3036656 will be estimated by calculating the ratio of the generalized least square means of AUC (0- τ) on Day 14 to AUC (0-inf) on 	

Pharmacokinetic Statistical Analyses (Time Invariance of GSK3036656 - Repeat Dose Study Phase)

Day 1, along with the corresponding 90% CI at each dose level.
--

Pharmacokinetic Statistical Analyses (Accumulation - Repeat Dose Study Phase)
--

Endpoint(s)

• AUC (Ro) and Cmax (RCmax)

Model Specification

 Will be statistically analysed using a mixed model (MM) using a log_e-transformation. Fixed effects : dose, day and dose*day Random Effect : Subject

 The Kenward and Roger method for approximating the denominator degrees of freedom and correcting for bias in the estimated variance-covariance of the fixed effects will be used. An unstructured covariance structure for the G matrix will be used. 
 In the event that this model fails to converge, alternative covariance structures may be considered such as VC or CS. Akaike's Information Criteria (AIC) will be used to assist with the selection of covariance structure.

Model Checking & Diagnostics

• Refer to Appendix 8 : Model Checking and Diagnostics for Statistical Analyses.
--

Model Results Presentation

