
 Reporting for tables, figures and formal statistical analyses : 
 Planned time relative to dosing will be used in figures, summaries, statistical analyses and calculation of any derived parameters, unless otherwise stated. The impact of any major deviation from the planned assessment times and/or scheduled visit days on the analyses and interpretation of the results will be assessed as appropriate. Reporting for Data Listings: 
 Planned and actual time relative to study drug dosing will be shown in listings (Refer to IDSL Statistical Principle 5.05.1). Unscheduled or unplanned readings will be presented within the subject's listings. Visits outside the protocol defined time-windows (i.e. recorded as protocol deviations) will be included in listings but omitted from figures, summaries and statistical analyses. 	
Unscheduled Visits	

 Unscheduled visits will not be included in summary tables. Unscheduled visits will not be included in figures. All unscheduled visits will be included in listings. 	
Descriptive Summary Statistics	
Continuous Data	Refer to IDSL Statistical Principle 6.06.1
Categorical Data	N, n, frequency, %
Reporting of Pharmacokinetic Concentration Data	
Descriptive Summary Statistics	Refer to IDSL Statistical Principle 6.06.1 and Standards for the Transfer and Reporting of PK Data using HARP.

Reporting Standards	
	For NQ values, refer to GUI_51487.
Reporting of Pharmacokinetic Parameters	
Descriptive Summary Statistics. (Log _e Transformed)	N, n, geometric mean, 95% CI of geometric mean, standard deviation (SD) of log transformed data and between subject geometric coefficient of variation (CVb (%)) will be reported. CVb (%) = $\sqrt{(\exp(SD^2) - 1) * 100}$ [NOTE: SD = SD of log _e transformed data]
Parameters Not Being Log _e Transformed	Tmax, t _{1/2}
Summary Tables	Cmax, t _{max} , AUC(0- τ), AUC(0-t), AUC (0- ∞), AUC (Ro), RCmax, C τ , t _{1/2} , Rss, Ae, fe, CLR, as data permit
Listings	Include PK Parameters Cmax, t _{max} , AUC(0- τ), AUC(0-t), AUC (0- ∞), AUC (Ro), RCmax, C τ , t _{1/2} , Rss, Ae, fe, CLR, as data permit
Graphical Displays	

 Refer to IDSL Statistical Principles 7.01 to 7.13 and Standards for the Transfer and Reporting of PK Data using HARP. 	

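### As written, the Part B Day 1 AUC(0-∞) used as reference for Rss and time invariance would include later doses; cut at the second dose, much of it is extrapolated.

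*SAP*

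**What the plan says.** Protocol section 10.3.2.2 and SAP section 7.2.1.3.2 assess time invariance as Day 14 AUC(0-τ) over Day 1 AUC(0-∞), on the log scale, with a 90% CI at each dose level: "AUC(0-inf) on Day 1 will be the reference phase in the analysis". SAP Table 5 defines Rss as the same ratio, and SAP section 2.2 lists Rss as a secondary endpoint.

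Table 5 is one table for both parts. Its AUC(0-t) runs "from time zero to the time of the last quantifiable concentration (C(t)) will be calculated" with linear-up, log-down trapezoids. AUC(0-∞) adds C(t)/λz. Neither entry stops at the next dose.

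Part B doses daily (Protocol section 4.2). Footnote 11 of the Part B schedule (Protocol section 7.1, SAP section 10.2.1) places Day 1 blood samples from pre-dose to 72 h, including 24, 36, 48 and 72 h.

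The documents also contain general safeguards:
- SAP section 7.2.1.3.1 says that the parameters "will be determined from plasma concentration-time data and urine concentration data, as data permits", and "Non-compartmental analysis will be performed in accordance with GSK PK Guidance document GUI_51487".
- SAP section 7.2.1.3.2 runs the statistical analyses only with sufficient data, explained as "if subjects have well defined plasma profiles".
- The protocol synopsis is permissive: "To estimate the pharmacokinetic linearity, the state ratio (R_{ss}) may be determined". Protocol section 10.3.2.2 is firmer and has Rss calculated.

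None of these gives a time cut for the Day 1 profile or a numeric limit on extrapolation.

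**The concern.** AUC(0-∞) after the first dose is meant to describe one dose. In Part B the 36 and 48 h samples follow the second dose, and the 72 h sample also follows the third. Table 5 applied as it stands puts those doses into the reference, both through the trapezoids and through the terminal slope. Rss then falls below its true value even when clearance has not changed. A low Rss is what rising clearance on repeat dosing would look like, so a secondary endpoint could point the wrong way.

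Cutting the profile at the second dose removes that error but leaves 24 h of data. Protocol section 4.1 predicts a half-life of about 30 h (range 12 to 72 h), so the window covers 24/72 = 0.33 to 24/12 = 2 half-lives. The reference then rests heavily on the extrapolated tail, and nothing in the plan tells the reader how heavily.

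**Working it through.** The plan states no figure for this analysis, so there is none to reproduce.

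**Inputs from the documents:** doses at 0, 24 and 48 h; the Day 1 sampling grid; the Table 5 formulas; half-lives of 12, 30 and 72 h. **Assumptions:** one compartment, linear kinetics, constant clearance, ka 0.5, 1 and 2/h, λz fitted to the last three points, the 24, 48 and 72 h samples drawn before that day's dose, and no assay error in steps 1 and 2.

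With dose/volume set to 1, one dose gives C(t) = ka/(ka − k) × (e^(−kt) − e^(−ka·t)), where k = ln 2/half-life, and the true AUC(0-∞) is 1/k.

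**1. Table 5 uncut.** Take a half-life of 30 h and ka 1/h: k = 0.0231, 1/k = 43.28, ka/(ka − k) = 1.0237. The last three concentrations are:
- 36 h: 1.0237 × (0.4353 + 0.7579) = 1.22
- 48 h: 1.0237 × (0.3299 + 0.5743) = 0.93
- 72 h: 1.0237 × (0.1895 + 0.3299 + 0.5743) = 1.12

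The profile rises between 48 and 72 h because drug accumulates. The fitted λz is 0.00094/h, so the tail is 1.12/0.00094 ≈ 1191, or 1191/43.28 = 27.5 times the true AUC(0-∞). Adding AUC(0-72), 1.53 times the true value, gives about 29.06 times. Rss = 1.00/29.06 = 0.03.

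All three half-lives at ka 1/h (AUCs relative to the true single-dose AUC(0-∞)):

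| Half-life | AUC(0-72) | Fitted λz (true), per h | AUC(0-∞) | Day 14 AUC(0-τ) | Rss |
|---|---|---|---|---|---|
| 12 h | 1.86 | 0.0151 (0.0578) | 3.19 | 1.00 | 0.31 |
| 30 h | 1.53 | 0.0009 (0.0231) | 29.06 | 1.00 | 0.03 |
| 72 h | 0.90 | −0.0062 (0.0096) | none | 0.96 | none |

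Over ka 0.5–2/h, Rss is 0.30–0.32 at 12 h and 0.03 at 30 h. At 72 h the slope has the wrong sign throughout. The true ratio is 1.00, 1.00 and 0.96; the last is below 1 because steady state is not quite reached by Day 14.

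**2. Cut at 24 h.** Error-free Rss is 0.94–1.00, so the cut removes the bias. The extrapolated share is (C(24)/k)/(1/k) = C(24). At ka 1/h:
- 12 h: 1.0613 × 0.25 = 0.265
- 30 h: 1.0237 × 0.574 = 0.588
- 72 h: 1.0097 × 0.794 = 0.801

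Over ka 0.5–2/h the shares are about 26–28%, 58–61% and 80–81%. The share passes one half at a half-life of about 22–24 h. If the daily dose is split in two, which Protocol section 4.2 allows, the window is 12 h and 2^(−12/half-life) gives 50%, 76% and 89%.

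**3. Precision after the cut.** With an assumed 10% CV on each concentration and three-point λz, the 5th to 95th percentiles of the geometric-mean Rss from 8 subjects are 0.93–1.04 at 12 h, 0.63–1.12 at 30 h and 0.54–1.45 at 72 h.

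**4. Whether Ro can stand in.** Under constant clearance, Ro = Day 14 AUC(0-τ)/Day 1 AUC(0-24): 1.00/(1 − 0.265) = 1.4, 1.00/(1 − 0.588) = 2.4 and 0.96/(1 − 0.801) = 4.8. Ro mixes accumulation with any change in clearance.

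**The case against.** The strongest reply is that the SAP hands non-compartmental conventions to GUI_51487. A stop at the next dose, λz criteria and an extrapolation limit are the kind of rule such guidance may hold. An experienced pharmacokineticist would probably cut at the second dose anyway. An Rss of 0.03, or a terminal phase that rises, would be conspicuous and would fail the SAP's own data-sufficiency condition. Part A data on at least three doses will also replace the predicted half-lives before Part B starts (Protocol section 6.3.2). All of this lowers the chance that a wrong Rss is reported. None of it changes what Table 5 says, and at 12 h a value near 0.3 is less obviously an artefact.

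Three stronger readings are tempting, and the documents do not support them.
- A reader might infer that the reported Rss will be wrong. That cannot be concluded without seeing GUI_51487.
- A reader might infer that all Part B AUC and half-life summaries are contaminated. SAP section 7.2.1.3.2 says only that summary statistics "will be calculated and tabulated by dose group for study Part A and Part B separately"; it names no day, and a Part B half-life could come from the Day 14 profile, which has 72 h of sampling after the last dose.
- A reader might infer that the SAP must carry a fixed extrapolation limit for each dose level. The documents give no basis for a value, so its absence alone is missing detail rather than an error.

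**Conclusion.** The point holds for one quantity: the Part B Day 1 AUC(0-∞) that serves as the Rss and time-invariance reference. The stated rule, read with the stated sampling and dosing, lets later doses into it. Under the assumptions above, unchanged kinetics would give an Rss of about 0.3 at a 12 h half-life, 0.03 at 30 h and no value at 72 h. Once cut, the ratio is close to unbiased but usable mainly at the short end of the predicted half-life range; at the predicted average more than half of the reference is extrapolated.

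The sizes depend on the one-compartment form, the three-point λz, the assumed error level and preclinical half-lives. The extrapolated shares depend little on ka. A minor-to-moderate correction is the right weight: Ro does not use AUC(0-∞), no escalation rule uses Rss, and no hypothesis is tested.

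**What to change.** 1. In SAP Table 5 and the time-invariance section, restrict Part B Day 1 AUC(0-t), λz and AUC(0-∞) to samples up to and including the one before the second dose, or before the next dose if the daily dose is divided. If GUI_51487 already requires this, say so there.
2. Report the percentage of Day 1 AUC(0-∞) that is extrapolated beside Rss for each dose level. Where most of it is extrapolated, label Rss as unreliable for time invariance, and note that Ro does not replace it.

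The cost is a few lines of SAP wording and one extra reported quantity, with no new samples. The downside is slightly more reporting, and Rss may prove uninformative at some dose levels.

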4.2. Part B (Repeat Dose)

Figure 2 Part B Schematic

Part B (Cohorts 3, 4, 5, and 6) will comprise up to 4 cohorts each containing 10 (8 active: 2 placebo) healthy adult subjects to examine the safety, tolerability and PK of a repeated daily dose of GSK3036656 over a period of up to 14 days. Progression to Part B from Part A will be based on an acceptable safety, tolerability and PK profile in Part A. Appropriate doses and dose regimens for Part B will be selected by the Dose Escalation Committee based on available safety, tolerability and PK data from Part A and/or any preceding repeat dose cohorts from Part B (Section 6.3). A decision to proceed to a higher dose in Part B will be based on the review of safety data from at least the first week of dosing and PK data from at least the first 48 hours of dosing at the preceding dose.

On Day –1 of each cohort, subjects will report to the unit for assessments and a meal. The subjects will then fast overnight (at least 8 hours) and be dosed the following morning (Day 1). Dosing with food may also be done if there are PK or tolerability reasons making it preferable to dose in a fed state. Dividing the total daily dose into 2 or 3 smaller doses administered over 24 hours may also be done. The decision to divide the total dose into smaller doses will be made by the GSK study team in conjunction with the Principal Investigator. Post-dose, subjects will undergo safety and PK assessments. Subjects will remain in the unit for at least 72 hours after the initial dosing. If they are released after that, it would be done at the discretion of the investigator following completion of assessments on Day 4 and provided there are no safety concerns. If released, subjects will then return to the clinical unit each morning to receive their daily dose and assessments for the duration of Part B. Dosing will be scheduled to occur at approximately the same time each day for each individual subject. Subjects will be required to spend at least the last 24 hours at the end of the dosing period in the unit in order to complete the necessary safety assessments and PK sampling. The subjects may then be discharged from the unit but, if discharged, will be required to return for additional PK sampling at 36, 48 and 72 hours post dosing. Approximately 14 days after their last dose, subjects will return to the unit for a follow-up visit.

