6.3. Planned Dose Escalation and Adjustments

After the initial dose of GSK3036656, the decision to proceed to each subsequent dose level will be made by the Dose Escalation Committee (DEC) based on safety, tolerability and preliminary pharmacokinetic data from the prior lower dose level (Further details regarding dose escalation can be found in the 201040 Dose Escalation Charter). In Part A, safety data for at least 5 days post-dose and PK data for at least 2 days (48 hours) postdose from at least 4 subjects who received active treatment at the prior lower dose level will be reviewed before dose escalation. In Part B, safety data for at least the first 1 week (7 days) of dosing and PK data for at least the first 2 days (48 hours) of dosing from at least 4 subjects who received active treatment at the prior lower dose level will be reviewed before dose escalation. The actual doses to be administered will be selected by the DEC and may involve either an increase or a decrease in the dose, or repeating the same dose.

The exposures (AUC, Cmax) expected with the next selected dose will be predicted by pharmacokinetic assessment and modelling, and by calculating Bayesian predictive probabilities as data permit (more details in Section 10.3.1).

In toxicology studies in dogs, heart valvular and vascular lesions have been observed at relatively high doses and exposures; no such lesions have been seen in rats at similar exposures. To avoid the risk of this adverse event in the FTIH subjects, exposures in the FTIH study will be limited to predefined levels. Based on discussions with the GSK Cardiovascular Safety panel, the study will aim to limit the maximum individual daily plasma AUC(0-24) and Cmax after single or repeat dose to 4.9 µg.h/mL and 0.443 µg/ml, respectively - a 30-fold margin from the corresponding dog NOAEL exposures of 147.0 µg.h/mL and 13.3 µg/ml at which no valvular or vascular lesions have been detected.

Note: The term “mean” applied to group human exposure parameters (e.g., AUC) in this section refers to Geometric Mean of a dose cohort.

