6.3.2. Dose escalation in Part B

Part B may be initiated after the safety and PK data of at least three doses from Part A are already known. The decision to initiate Part B will be made by the GSK Study team in conjunction with the investigator.

The following rules will guide dose selection in Part B:

1. The starting daily dose in Part B will be selected such that its expected exposure (mean AUC[0-24] or Cmax) on the last day of dosing is no higher than the Day 1 exposure of a dose that has been found to be safe and well tolerated in Part A. The expected daily exposures during the dosing period, including on the last day of dosing, will be predicted based on the PK parameters for GSK3036656 established in Part A. As the highest exposure with repeat dosing is expected on the last day of dosing (as a result of accumulation), this approach would select a daily dose which provides systemic concentrations that, at any time during the period of dosing, are not likely to be higher than the ones already found to be safe and well tolerated in Part A.
2. Subsequent doses in Part B may be selected using the criteria described above for the starting dose in Part B. The expected daily exposures during the dosing period, including on the last day of dosing, will be predicted based on available PK data from Part A and from prior cohorts in Part B. Alternatively, a dose may also be selected even if it does not meet these criteria provided it is no more than 4-fold higher than a previous dose that has been found to be safe and well tolerated upon repeat dosing in Part B.
3. The highest daily dose in Part B will not exceed the highest single dose that has been found to be safe and well tolerated in Part A.
4. A proposed dose will be acceptable if the predicted probability of an individual exceeding a daily plasma AUC (0-24) of 4.9 $\mu\text{g.h/mL}$ or Cmax of 0.443 $\mu\text{g/mL}$ on any day of the dosing period, as estimated by PK modeling and Bayesian analysis (if feasible), is no more than 10%.

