A statistical analysis will be performed using the power model. The analysis will be performed on \log_e -transformed data. For each of these parameters a mixed effects model will be fitted with \log_e (dose) as a fixed effect and individual subject fitted as random effects. Estimates of the mean slopes of \log_e (dose) will be reported along with corresponding 90% confidence intervals (slope ≈ 1 implies dose proportionality).

Food Effect (Single Dose Study)

The effect of food on the pharmacokinetics of GSK3036656 will be examined. AUC(0-t), AUC(0- ∞), Cmax, and $t_{1/2}$ of GSK3036656 will be analysed after a \log_e -transformation of the data. An analysis of variance model will be fitted along with 90% confidence intervals using a mixed effects model, with fed/fasted condition as a fixed effect and subject as a random effect. Point estimates and corresponding 90% confidence intervals will be constructed for the comparisons of interest of GSK3036656 fed – GSK3036656 fasted, using the residual variance. These will then be back-transformed to provide point estimates and corresponding 90% confidence intervals for the geometric mean ratios fed:fasted.

Tmax will be analyzed non-parametrically using a Wilcoxon matched pairs test to compute the point estimate and 90% confidence interval for the median difference (fed – fasted).

Accumulation (Repeat Dose Study Phase)

The extent of accumulation of GSK3036656 will be based on AUC (Ro) and Cmax (RCmax).

The focus of the statistical analysis will be to estimate the accumulation ratio, Ro, on the pharmacokinetics of GSK3036656. Following \log_e -transformation, AUC(0- τ) on Day 14 and AUC(0- τ) on Day 1 will be analysed by a mixed effect model, fitting fixed effect terms for dose, day, and day by dose interaction, and fitting subject as a random effect. For each dose, point estimates and 90% confidence intervals for the differences “Day 14- Day 1” will be constructed using the appropriate error term. The point estimates and associated 90% confidence intervals will then be exponentially back-transformed to provide point and 90% confidence interval estimates for the ratios “Day 14: Day 1” for each active dose. If both the dose and day by dose interaction terms are not significant, a single point estimate and confidence interval pooled across all doses will also be constructed.

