
 Point estimates and 90% confidence intervals for the differences “Day 14- Day 1” will be constructed using the appropriate error term. The point estimates and associated 90% confidence intervals will then be exponentially back-transformed to provide point and 90% confidence interval estimates for the ratios “Day 14: Day 1” for each active dose. If both the dose and day by dose interaction terms are not significant, a single point estimate and confidence interval pooled across all doses will also be constructed.
--

Pharmacokinetic Statistical Analyses (Achievement of Steady State - Repeat Dose Study Phase)

Endpoint(s)

• Trough plasma concentrations at the end of the dosing interval (C _T)
--

Model Specification

 Will be statistically analysed using a mixed models (MM) using log-transformed dose data. Fixed effects : dose, day and dose*day Random Effect : Subject

 The Kenward and Roger method for approximating the denominator degrees of freedom and correcting for bias in the estimated variance-covariance of the fixed

Pharmacokinetic Statistical Analyses (Achievement of Steady State - Repeat Dose Study Phase)

effects will be used.

- An unstructured covariance structure for the G matrix will be used.
 - In the event that this model fails to converge, alternative covariance structures may be considered such as VC or CS.
 - Akaike's Information Criteria (AIC) will be used to assist with the selection of covariance structure.

Model Checking & Diagnostics

- Refer to [Appendix 8: Model Checking and Diagnostics for Statistical Analyses](#).

Model Results Presentation

The coefficients of the slopes for the day effect for each dose, along with corresponding 90% confidence intervals, will be used to determine whether steady state was achieved. If the day-by-dose interaction were not significant, then the point estimates and 95% CIs for the individual dose levels will also be pooled across all doses for a single D14/D1 ratio.

Trough concentration levels collected pre-morning dose will be plotted by collection day and dose.

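### The pooled accumulation ratio is made conditional on a non-significant dose main effect, which has no bearing on whether the Day 14:Day 1 ratio is common across doses and will usually block pooling

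*SAP*

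**What the plan says.** SAP 7.2.1.3.2 (Accumulation, repeat dose phase) specifies a mixed model on the log scale with "Fixed effects : dose, day and dose*day" and subject as a random effect. Protocol 10.3.2.2 says the same of AUC(0-τ) on Days 1 and 14, which "will be analysed by a mixed effect model, fitting fixed effect terms for dose, day, and day by dose interaction", and extends the analysis to Cmax. Neither document dose-normalises the response.

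The main output is by dose. "Point estimates and 90% confidence intervals for the differences" between Day 14 and Day 1 are back-transformed to a ratio for each active dose. A pooled ratio is then added under the condition "If both the dose and day by dose interaction terms are not significant, a single point estimate and confidence interval pooled across all doses". The protocol has the same condition: "If both the dose and day by dose interaction terms are not significant". Neither document gives a significance level for these tests.

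The steady-state analysis of trough concentrations, in the same sections of both documents, also has dose, day and their interaction as fixed effects. There, pooling across doses depends on the interaction alone.

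**The concern.** A common accumulation ratio means that the Day 14 minus Day 1 difference in log exposure is the same at every dose. In this model that is exactly the absence of a day-by-dose interaction. The dose main effect describes something else: whether exposure, averaged over the two days, differs between dose levels. In an escalation study it should differ, and the plan's own dose-proportionality analysis regards a log-log slope near 1 as the proportional case.

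The rule therefore tends to withhold the pooled ratio when exposure rises with dose as expected. It tends to allow it when exposure is flat, the doses are close together or the data are noisy. Extent of accumulation is a stated secondary objective. At stake is whether the study summarises it with all active Part B subjects or only in groups of 8.

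**Working it through.** The documents give no figure on this point, so there is nothing to reproduce. Two quantities were calculated: how often the dose condition blocks pooling, and what precision is lost when it does.

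**Inputs from the documents**
- Part B has "up to 4 cohorts each containing 10 (8 active: 2 placebo) healthy adult subjects" (Protocol 4.2), so n = 8 per dose and k is at most 4.
- Dose steps are not fixed. One selection route allows a dose "provided it is no more than 4-fold higher than a previous dose" (Protocol 6.3.2), and the committee's choice "may involve either an increase or a decrease in the dose, or repeating the same dose" (Protocol 6.3).
- The only CV given is 50% for clearance, used in the sponsor's simulations (Protocol 4.5). Protocol 10.2 says no human PK variability data exist.
- The confidence level is 90%.

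**Assumptions**
- Exposure is proportional to dose, and each trial uses k distinct, equally spaced (fold) doses.
- Between-subject CV is 30–50% and within-subject CV 15–30%.
- Tests are at 5%.

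**Chance that the dose term is non-significant**

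The dose term is tested between subjects. Each subject contributes the mean of two log values, with variance V = σb² + σw²/2, where σ² = ln(1 + CV²). The test follows a noncentral F with k−1 and 7k degrees of freedom and noncentrality λ = 8·Σ(μi − μ̄)²/V, where μi = ln(dose i).

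At between-subject CV 50% and within-subject CV 20%, V = 0.2231 + 0.0392/2 = 0.2428.
- 4 doses, 2-fold: Σ = 5(ln 2)² = 2.402; λ = 8 × 2.402/0.2428 = 79.2; non-significant in under 0.01%.
- 3 doses, 2-fold: Σ = 2(ln 2)² = 0.961; λ = 31.7; 0.2%.
- 2 doses, 2-fold: Σ = 0.5(ln 2)² = 0.240; λ = 7.9; 26%.
- 4 doses, 1.5-fold: Σ = 5(ln 1.5)² = 0.822; λ = 27.1; 1.0%.
- 3 doses, 1.5-fold: Σ = 2(ln 1.5)² = 0.329; λ = 10.8; 21%.

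Over the full assumed CV ranges, the probability that the dose term is non-significant is:

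| Cohorts | 1.5-fold steps | 2-fold steps | 4-fold steps |
|---|---|---|---|
| 2 | 32–69% | 1.5–29% | at most 0.13% |
| 3 | 0.6–25% | at most 0.4% | under 0.01% |
| 4 | at most 1.7% | under 0.01% | under 0.01% |

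Close spacing weakens the block. With 4 cohorts at 1.25-fold and between-subject CV 50%, the dose term is non-significant in 38–44%. A less-than-proportional slope of 0.7 (between-subject CV 50%, within-subject CV 20%) gives 0.06% for 4 cohorts at 2-fold and 18% at 1.5-fold. A 10% test level makes the dose condition harder to meet: 3 cohorts at 1.5-fold falls from 21% to 12%.

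The whole two-part rule was also simulated with a truly common ratio (between-subject CV 50%, 20,000 trials per scenario). It allowed pooling in 0.0% (4 cohorts, 2-fold), 1.0% (4 cohorts, 1.5-fold), 0.2% (3 cohorts, 2-fold) and 24% (2 cohorts, 2-fold). A rule on the interaction alone allowed it in about 95% of trials in each case.

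**Precision lost**

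The log-scale half-width of the 90% CI is t(0.95, 7k)·σw·√(2/8) per dose and t(0.95, 7k)·σw·√(2/(8k)) pooled. Their ratio is √k: 1.41, 1.73 and 2 for k = 2, 3 and 4.

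With k = 4 and within-subject CV 20%, t = 1.701 and σw = 0.198:
- per dose: 1.701 × 0.198 × 0.5 = 0.168, a factor of ×/÷1.18;
- pooled: 1.701 × 0.198 × 0.25 = 0.084, a factor of ×/÷1.09.

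**The case against.** The strongest reply is that nothing planned as a main result is lost. The ratio with its 90% CI is reported for each active dose in every case, and the pooled value is described as an addition. The mock table PK_T5 is laid out by treatment with no pooled row. Ro and RCmax are also summarised by dose group with geometric means and 95% CIs. No hypothesis is tested, and Part B dose selection uses predicted exposures rather than a pooled Ro. All of this stands, and it limits the point to precision on a supplementary summary of a secondary endpoint.

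A second reply is that the number and spacing of doses are open. Part B may run fewer than 4 cohorts, and doses may be close together, lowered or repeated. This also stands. A reader might infer that the condition almost never holds, or that pooling would occur in under 0.5% of trials with 3–4 doses whatever the steps. The documents do not support that, because they do not fix the spacing: 3 cohorts at 1.5-fold with between-subject CV 50% leave the dose term non-significant in 20–25% of trials.

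A reader might also infer that the best estimate is discarded. It is simply not constructed, it could be calculated later from the same data, and it is the better summary only if the ratio really is common. With 8 subjects per dose, a non-significant interaction does not prove that.

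Neither reply justifies the dose condition. It is irrelevant to a common ratio under any spacing, and the plan's own steady-state rule does without it.

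**Conclusion.** The point holds as an error in the pooling rule, in both documents and for both Ro and RCmax. The error itself needs no numerical assumption: on un-normalised log exposure, the dose main effect does not bear on whether accumulation is common to all doses.

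How often it matters does depend on assumptions (proportional exposure, 8 active per cohort, 5% level, between-subject CV 30–50%, within-subject CV 15–30%). The dose condition then blocks pooling in:
- at least 99.6% of trials with 3–4 cohorts at 2-fold steps or wider;
- over 98% with 4 cohorts at 1.5-fold;
- 75–99% with 3 cohorts at 1.5-fold;
- 71–98% with 2 cohorts at 2-fold;
- fewer with closely spaced or repeated doses.

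The consequence is wider intervals, by up to a factor of 2 on the log scale with 4 cohorts and a common ratio. There is no bias, and no effect on dose escalation. It is a modest correction, worth making because it costs so little.

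**What to change.** In SAP 7.2.1.3.2 and Protocol 10.3.2.2 (Accumulation), delete the dose-term condition and state the level of the remaining test. Suggested wording: *When the day-by-dose interaction is not significant at the [stated] level, one Day 14:Day 1 ratio with its 90% CI, pooled over doses from the model with dose and day, will also be reported for AUC(0-τ) and for Cmax.*

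Keep the per-dose ratios in all cases, so that any difference between doses that the interaction test misses stays visible. Add a pooled row to mock table PK_T5.

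The cost is one clause in each document and one table row. No data, subjects or assessments are added.
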